2.7.2 Safety Outcome Measures

The safety outcome measures in this study are:

- The number, frequency, and severity of adverse events (AEs) collected from the time of first treatment until 12 weeks after study treatment completion to evaluate safety of leronlimab (PRO 140) in subjects with CCR5+ locally advanced or metastatic solid tumors.

Note: Adverse events will follow National Cancer Institute Common Terminology Criteria for Adverse Events (CTCAE) version 5.0

- Laboratory data changes from baseline to subsequent scheduled visits
- Changes in physical examinations from baseline to subsequent scheduled visits

- Changes in vital signs from baseline to subsequent scheduled visits.
- Changes in Eastern Cooperative Oncology Group (ECOG) performance status from baseline to subsequent scheduled visits.
- Changes of electrocardiogram (ECG) results from baseline to subsequent scheduled visits

2.7.3 Exploratory Outcome Measures

- Measure immune biomarkers in CTCs, metastatic tissue and immune cells such as CAML and correlate with therapeutic benefit (PFS); and
- Assess changes in CTCs and CAML after treatment and perform correlative analysis of CCR5 expression

3. Sample Size Determination, Statistical Power, And Significance Level

This is a multicenter study and up to 30 subjects will be enrolled in this study. The sample size for is based on clinical judgment. No statistical power calculation is used to establish the sample size.

4. INTERIM ANALYSIS

No Interim Analysis (IA) will be performed.

5. PRIMARY HYPOTHESIS TO BE TESTED

There is no formal hypothesis testing for this study as the study is a Phase I/Phase II evaluation and is not intended to be hypothesis generating. The study is not powered to reliably yield statistically significant conclusions.

6. ANALYSIS POPULATIONS

6.1 Evaluable population

The Evaluable population is defined as the set of subjects who have received at least one dose of leronlimab (PRO 140) and have measurable disease at baseline. This population will be used for the analysis of efficacy parameters or measurements.

6.2 Per Protocol (PP) Population

The Per Protocol (PP) population is defined as the set of subjects who meet the Evaluable Population requirements and were not associated with any major protocol violations. This population will be identified before the database lock

6.3 Safety Population

The Safety Population will include all subjects who have received one dose of leronlimab (PRO 140).

This population will be used for the analysis of safety parameters or measurements

7. DATA CONVENTION AND RELATED DEFINITIONS

7.1 Baseline Definition

For all parameters, baseline will be defined as the last available value before the first treatment.

7.2 Duplicate Data

For unplanned duplicate data within a protocol-specified visit, all collected data will be listed and the last measured value will be used for the analysis. If it is not possible to identify the “last measured value,” the average of the duplicate values will be used.

7.3 Outliers

Data points that appear to be outliers (i.e., clinically identified to be too small or too large) will be investigated and will not be excluded from the listings. If the clinician confirms that a data point is truly an outlier and is not clinically possible, two analyses will be performed, one with the outlier data point and one without it. Any such analysis will be clearly indicated and footnoted.

7.4 Handling of Missing Data

Every effort will be made to obtain required data at each scheduled evaluation from all subjects who have been randomized to minimize missing data. Missing data will not be imputed.

7.5 Sensitivity Analysis

7.6 Multicenter Clinical Trials

This is a multi-center clinical trial with up to 10 centers in the United States (US).

7.7 Multiple Comparisons and Multiplicity

There will be no adjustment for multiple testing or multiplicity for this phase II trial. For all effectiveness endpoints, inference will be based on type I error rate of 0.05.

7.8 Covariates and Prognostic Factors

In the efficacy analysis, the baseline values will be used as covariates in the analysis of all efficacy outcome measures.

7.9 Subgroups

There is no prespecified subgroup analysis for this study. Subgroup analysis may be conducted as needed.

7.10 Standard Calculations

7.10.1 Age

Age will be calculated according to the formula noted below.

$$\text{Age (years)} = \text{integer of } [(date \text{ of informed consent} - date \text{ of birth}) / 365.25]$$

7.10.2 Body Mass Index (BMI)

BMI will be calculated using height (in cm) and weight (in kg) according to the formula noted below.

$$\text{BMI (kg/m}^2\text{)} = \text{Weight (kg)}/[\text{Height (cm)}/100]^2$$

7.10.3 Change from baseline

Change from baseline will be calculated for each post baseline visit as follows:

$$\text{Change From Baseline} = \text{Post baseline result at time} - \text{Baseline result}$$

7.10.4 Percent Change from Baseline

Percent change from baseline will be calculated according to the formula noted below.

$$\text{Percent change from Baseline} = (\text{Post baseline result at time} - \text{Baseline result}) / \text{Baseline result} * 100$$

7.10.5 Time to Progression Free Survival (PFS)

Time to Progression Free Survival (PFS) in months will be calculated according to the formula noted below:

$$\text{Time to Progression Free Survival} = (\text{Date of objective disease progression or death due to any cause, whichever occurs earlier} - \text{Date of first treatment} + 1)/30.4$$

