8.6.3. Missing Data

All data will be used as observed, and no imputations will be made for any missing data point for early phase study.

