7.10.6 Time to new metastases (TTNM)

Time to new metastases (TTNM) will be calculated according to the formula noted below:

$$\text{Time to new metastases (TTNM)} = (\text{Date of new metastases} - \text{Date of first treatment}) + 1$$

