7.10.7 Time to Overall Survival (OS)

Time to Overall Survival (OS) in months will be calculated according to the formula noted below:

$$\text{Time to Overall Survival} = (\text{Date of death due to any cause} - \text{Date of first treatment} + 1)/30.4$$

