8. STATISTICAL METHODS

All statistical analyses will be performed using SAS® for Windows, version 9.4 or later. All data collected during this study will be presented in subject data listings.

All the efficacy analyses presented here will be conducted using ITT and PP populations. All safety analyses will be conducted using the Safety population.

For continuous variables, descriptive statistics (n, mean, standard deviation, median, minimum and maximum) will be presented by treatment group. For categorical variables both frequencies and percentages will be presented by treatment group.

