8.2.1.1 Progression free survival (PFS)

The time to progression free survival in months will be calculated using the formula in [Section 7.10.5](#) and summarized descriptively.

The likelihood score test in the Cox proportional hazards model (which is the equivalent of the Log Rank test) will be used to compare the time to progression free survival between the treatment groups. Kaplan-Meier analysis will be used to depict the median time (days) to progression free survival.

The Progression free survival (PFS) will be presented and summarized descriptively.

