8.2.1.3 Time to new metastases (TTNM)

The Time to new metastases will be calculated using the formula in [Section 7.10.6](#) and summarized descriptively.

The likelihood score test in the Cox proportional hazards model (which is the equivalent of the Log Rank test) will be used to compare the time to new metastases between the treatment groups. Kaplan-Meier analysis will be used to depict the median time (days) to new metastases.

The proportion of new metastases will be presented and summarized descriptively.

8.2.1.4 Change from baseline in circulating tumor cells (CTC) level in the peripheral blood

The change from baseline in circulating tumor cells (CTC) level in the peripheral blood will be summarized descriptively and will be compared using ANCOVA.

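### The PFS, TTNM and OS formulas give a time only to patients with the event, and the SAP also orders plain descriptive summaries of those times, which come out short

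*SAP*

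**What the plan says.** The three formulas in the SAP each subtract the first-treatment date from an event date:

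- PFS (SAP 7.10.5): "Date of objective disease progression or death due to any cause, whichever occurs earlier", in months.
- TTNM (SAP 7.10.6): "Date of new metastases", with no divisor, so in days.
- OS (SAP 7.10.7): "Date of death due to any cause", in months.

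Neither document names an end date for a patient without the event. On missing values, SAP 7.4 says "Missing data will not be imputed", and Protocol 8.6.3 agrees.

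SAP 8.2.1.1, 8.2.1.3 and 8.2.1.5 say that each formula time is to be summarised descriptively. SAP 8 fixes what that means: "For continuous variables, descriptive statistics (n, mean, standard deviation, median, minimum and maximum) will be presented by treatment group". A separate sentence in each of the three sections orders a Kaplan-Meier median in days. Protocol 8.7.3 also relies on Kaplan-Meier for all three endpoints. SAP 2.7.1 and Protocol 8.7.3 add that an average survival time will be measured, and they put every dosed patient in the primary PFS analysis.

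**The concern.** A patient who has not progressed, developed a new metastasis or died gets no value from these formulas. The mean and median of the values that remain describe only patients whose event was seen, and long times are the ones most likely to be absent. The report could then show two medians for one endpoint, in different units, with the event-only one too low. The average survival time would be affected as well.

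Event-free patients are foreseeable. Survival follow-up stops 2 years after treatment discontinuation (SAP 2.1), and withdrawal of consent ends follow-up (Protocol 5.1). After treatment, imaging until progression is specified only for patients who stop for adverse events without progression (Protocol 4.4). A patient who dies without a new metastasis also has no TTNM.

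The Kaplan-Meier analysis has a related gap. It needs a time for each event-free patient, and no rule supplies one.

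**Working it through.** The plan states no expected median, event count or event-free share, so there is no figure of its own to reproduce. Every median and loss rate below is an assumption; only the 2-year follow-up rule and the 30 patients come from the documents.

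**OS, no dropout.** Let OS = P + Q, where P is time to progression (exponential, rate a = ln 2 / PFS median) and Q is survival after progression (exponential, rate b). Treatment is assumed to stop at progression, so death is observed only if Q ≤ 24 months.

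- b solves (b·exp(−at) − a·exp(−bt)) / (b − a) = 0.5 at t = the true OS median.
- Event-free share = exp(−24b).
- Event-only mean = 1/a + 1/b − 24·exp(−24b) / (1 − exp(−24b)).
- The event-only median solves P(P + Q ≤ t, Q ≤ 24) / (1 − exp(−24b)) = 0.5 numerically.

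Example with PFS 4 and OS 12: 1/a = 5.77, b = 0.1155, 1/b = 8.66, and the event-free share is 0.0625. The mean is 14.43 − 24 × 0.0625 / 0.9375 = 14.43 − 1.60 = 12.83.

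| PFS / OS median (months) | b | Event-free | Event-only median | Short by | Event-only mean | True mean | Short by |
|---|---|---|---|---|---|---|---|
| 4 / 12 | 0.1155 | 6% | 11.3 | 6% | 12.8 | 14.4 | 11% |
| 6 / 12 | 0.1733 | 2% | 11.8 | 2% | 14.0 | 14.4 | 3% |
| 4 / 24 | 0.0392 | 39% | 15.0 | 37% | 15.9 | 31.3 | 49% |
| 6 / 24 | 0.0474 | 32% | 17.0 | 29% | 18.4 | 29.7 | 38% |

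In simulated trials of 30 patients with event-free patients kept as censored, the typical event-only and Kaplan-Meier medians, in table order, are 11.3 and 12.0, 11.8 and 12.0, 15.1 and 23.8, and 17.0 and 24.0.

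**OS, random loss.** If loss raises the event-free share to 20% at a true OS median of 12, the event-only median is 10.5 (PFS 4) or 10.7 (PFS 6), which is 13% or 11% short.

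**PFS, random loss.** With event rate λ and independent exponential loss at rate μ, times among patients with the event are exponential with rate λ + μ, and the event-free share is c = μ / (λ + μ). The event-only mean and median are therefore (1 − c) times the true values. With c = 0.20, medians of 4 and 6 become 3.2 and 4.8, which is 20% short.

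**PFS, full follow-up to an assumed 28 months.** The event-free share is exp(−28λ) = 0.8% or 3.9%. The event-only medians are 3.96 and 5.67 (1% and 6% short). The event-only means are 5.55 and 7.51, against true means of 5.77 and 8.66.

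TTNM is not quantified, because its result depends on how death is handled, which the plan leaves open.

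**The case against.** The strongest reply is that the orders can be read together. The SAP never says that the summaries are unadjusted. The same sections require Kaplan-Meier medians, Protocol 8.7.3 bases PFS, TTNM and OS on Kaplan-Meier curves, and Kaplan-Meier presupposes times for event-free patients. The average survival time is an endpoint note, not a method. What stands of this is that the Kaplan-Meier medians remain planned and are not biased by the event-only formulas. What does not stand is that the descriptive summary simply means Kaplan-Meier. The SAP orders the two in separate sentences, and the general rule in SAP 8 gives the first one a mean and a median.

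Three stronger readings are tempting and fail:

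- A reader might infer that the no-imputation rules forbid censored times. Protocol 8.6.3 says "All data will be used as observed, and no imputations will be made for any missing data point for early phase study", but censoring is not imputation, so neither rule bars it.
- A reader might infer that the event-only mean must fall below the Kaplan-Meier median. It need not, because the times are skewed. At a true OS median of 12 the means are 12.8 and 14.0, against Kaplan-Meier medians of about 12. The PFS means of 5.55 and 7.51 lie above the medians of 4 and 6.
- A reader might take the 29% to 49% shortfalls as the expected size. They require a true OS median of 24 months, which no figure in the documents supports; eligibility asks only for a life expectancy of at least 6 months. Protocol 7.15.6 also lets some patients continue treatment beyond progression, which moves the 2-year window later and would reduce the OS shortfall.

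The study is also single-arm, unpowered and without formal hypothesis testing, which limits the harm of an extra descriptive line.

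**Conclusion.** The point holds as a should-fix. Followed as written, the SAP produces event-only summaries of PFS, TTNM and OS. Their means lie below the true means, and their medians lie below the true and Kaplan-Meier medians. The OS shortfall is small if nearly all patients die within follow-up and large if many do not: about 2% to 6% (median) and 3% to 11% (mean) at a true OS median of 12 months, and 29% to 37% and 38% to 49% at 24 months. Random loss leaving 20% event-free takes 20% off the PFS median. These sizes assume exponential times, treatment stopped at progression and, for the OS ranges, no dropout.

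The documents do not support the conclusion that the Kaplan-Meier results are biased short by this. Their defect is that event-free patients have no stated end date although every dosed patient must enter the PFS analysis, so the censoring date would have to be chosen by whoever programs the analysis.

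**What to change.** - Delete the plain descriptive summaries of the three times in SAP 8.2.1.1, 8.2.1.3 and 8.2.1.5.
- Replace the average survival time (SAP 2.7.1, Protocol 8.7.3) with the Kaplan-Meier median and 95% confidence interval, plus the numbers of events and censored patients. A restricted mean at a stated horizon is an option.
- Redefine SAP 7.10.5 to 7.10.7 as time to event or censoring: PFS and TTNM censored at the last adequate tumour assessment, OS at the last date known alive.
- For TTNM, state how death without a new metastasis is handled as a competing event. The rule must not extend time at risk only for patients who die. Counting death as competing only when it falls within, say, 6 months of the last scan does exactly that. With assumed independent exponential times (new-metastasis and death medians 12 months, scanning-stop median 4), the true 12-month incidence of new metastasis is 0.5 × (1 − 0.25) = 37.5%, and that rule gave 25% to 28% in simulation.
- State the limit on TTNM set by scanning that mostly ends with treatment.
- Use one time unit throughout; months and days are now mixed.

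The cost is SAP wording, one matching sentence in the protocol, and derivation code. No new data are needed, since scans, survival contacts and deaths are already collected (Protocol 4.4 and 4.4.2). SAP 12 describes the document as a first draft, so the change is cheap now.

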7.10.6 Time to new metastases (TTNM)

Time to new metastases (TTNM) will be calculated according to the formula noted below:

$$\text{Time to new metastases (TTNM)} = (\text{Date of new metastases} - \text{Date of first treatment}) + 1$$

7.10.7 Time to Overall Survival (OS)

Time to Overall Survival (OS) in months will be calculated according to the formula noted below:

$$\text{Time to Overall Survival} = (\text{Date of death due to any cause} - \text{Date of first treatment} + 1)/30.4$$

7.10.8 Overall Response Rate (ORR)

Overall Response Rate will be calculated according to the formula noted below:

Overall Response Rate (ORR) = Complete Response (CR) + Partial Response (PR)

7.10.9 Clinical Benefit Rate (CBR)

Clinical Benefit Rate (CBR) will be calculated according to the formula noted below:

Clinical Benefit Rate (CBR) = Complete Response (CR) + Partial Response (PR) +
Stable Disease (SD)

8. STATISTICAL METHODS

All statistical analyses will be performed using SAS® for Windows, version 9.4 or later. All data collected during this study will be presented in subject data listings.

All the efficacy analyses presented here will be conducted using ITT and PP populations. All safety analyses will be conducted using the Safety population.

For continuous variables, descriptive statistics (n, mean, standard deviation, median, minimum and maximum) will be presented by treatment group. For categorical variables both frequencies and percentages will be presented by treatment group.

8.1 Summarizing Disposition and Baseline Data

8.1.1 Subject Disposition and Withdrawals

There will be a detailed accounting of all subjects who sign an informed consent to participate in this trial. The following will be summarized by treatment group:

- The number of subjects who signed informed consent
- The number of subjects who are screen failures
- The number of subjects who received at least one study treatment
- The number of subjects who completed the study
- The number of subjects who discontinued prior to completion
 - Reasons for discontinuation prior to completion will also be summarized descriptively by treatment group.

The number of subjects in each analysis population will be summarized, reason for exclusion from analysis populations will be listed.

In addition, there will also be a listing of all subjects, which will provide the clinical trial center, treatment group, study completion status and the specific reason for discontinuation.

8.1.2 Protocol Deviations

Protocol deviations will be identified and classified as minor or major before un-blinding.

Protocol deviations for all randomized subjects will be listed as by-subject listing and major deviations will be summarized descriptively according to the following categories:

- Informed consent not properly attained
- Did not meet Inclusion/Exclusion criteria but entered into study
- Developed withdrawal criteria during the study but not withdrawn
- Procedure performed out of window
- Received excluded concomitant medication
- Missed procedure or visit

8.1.3 Demographics and Baseline Characteristics

Demographics and baseline characteristics (including age, race, gender, disease characteristics etc.) will be presented as by-subject listing and summarized in Safety population. See [Section 7.1](#) for baseline definition.

Tumor Imaging Assessment, Serum Pregnancy Test, and Tissue for CCR5 will be provided as by-subject listings.

8.1.4 Medical History

Medical history will be coded using the most current available version of Medical Dictionary for Regulatory Activities (MedDRA) and will be summarized by by system organ class (SOC) and preferred term (PT). Each subject will be counted only once within each PT or SOC.

8.1.5 Prior and Concomitant Medications

Prior medication is defined as any medications with an end date prior to the first treatment date.

All prior and concomitant medications recorded in the case report form will be listed and coded to the drug substance level (i.e., generic term) using the most recent version of WHO Drug dictionary, and summarized by treatment group and by the number and percentage of subjects taking each medication for the Safety population.

8.1.6 Extent of Exposure

All treatment administration data will be listed and summarized for the Safety population.

The duration (in days) of treatment administration will be determined per the following formula:

| |
|--|
| Duration = (date of last treatment administration – date of first treatment administration + 1 |
|--|

8.1.7 Study Treatment Compliance

Study treatment compliance will be determined per the following formula:

Compliance = [sum of all study drugs administered/ sum of all study drugs prescribed during the Duration of Exposure] x 100%

All accountability and compliance data will be listed and summarized for the Safety population.

8.2 Analysis of Efficacy Data

The efficacy analysis will be conducted on the Evaluable Population. The PP population will be used as a supportive analysis if there is at least 5% difference between the numbers of subjects in the two populations. Any observations excluded from the efficacy analyses will be listed as by-subject listings.

8.2.1 Primary Endpoint / Outcome Measure

All data from this endpoint will be presented as by-subject listing.

8.2.1.1 Progression free survival (PFS)

The time to progression free survival in months will be calculated using the formula in [Section 7.10.5](#) and summarized descriptively.

The likelihood score test in the Cox proportional hazards model (which is the equivalent of the Log Rank test) will be used to compare the time to progression free survival between the treatment groups. Kaplan-Meier analysis will be used to depict the median time (days) to progression free survival.

The Progression free survival (PFS) will be presented and summarized descriptively.

8.2.1.2 Overall response rate (ORR) and clinical benefit rate (CBR)

The Overall response rate (ORR) and clinical benefit rate (CBR) will be calculated using the formula in [Section 7.10.7](#) and [7.10.8](#), and summarized descriptively.

8.2.1.3 Time to new metastases (TTNM)

The Time to new metastases will be calculated using the formula in [Section 7.10.6](#) and summarized descriptively.

The likelihood score test in the Cox proportional hazards model (which is the equivalent of the Log Rank test) will be used to compare the time to new metastases between the treatment groups. Kaplan-Meier analysis will be used to depict the median time (days) to new metastases.

The proportion of new metastases will be presented and summarized descriptively.

8.2.1.4 Change from baseline in circulating tumor cells (CTC) level in the peripheral blood

The change from baseline in circulating tumor cells (CTC) level in the peripheral blood will be summarized descriptively and will be compared using ANCOVA.

